NCT03756571

ANALYSIS PAN

Cerebral Palsy: Ankle Foot Orthoses - Footwear Combinations

August 7, 2018

Analysis Plan:

For both Specific Aims, our primary analysis will be an intent-to-treat analysis using outcomes collected during the parallel group RCT phase, (i.e., before TSAFO group crosses over to AFO-FC). This will be cross-sectional analysis based on linear regression models in which outcomes at primary endpoint of T1 (3-month) are the dependent variables, group indicator is the predictor of interest, with including baseline outcomes, and biomarkers of age, gender, gait pattern (equinus or crouch) and GMFCS. A secondary repeated measure analysis based on mixed effects models will also be conducted to examine the changes in outcomes across all 3 time points (T0, T1 and T2). In this analysis, group indicator will be entered as a time-varying predictor given the waitlist design (for AFO-FC group the indicators take values (0, 1, 1), whereas for TSAFO group the indicators take values (0, 0, 1)), time will be modelled as a discrete variable, and between group differences will be examined by group-by-time interactions and likelihood ratio test.

Study Design and Randomization.

A randomized waitlist trial [38] will be used to compare the AFO-FC to TSAFO (See Fig. 4). After enrollment, subjects are randomized to either wearing the AFO-FC (the intervention group) or TSAFO (waitlist group). There will be three main time points for assessment (T0, T1, T2) with the initial baseline assessment (T0) split over 2 visits. The first baseline visit includes consent, randomization, casting for orthoses (AFO-FC or TSAFO), and completion of parental report surveys (physical activity, function, satisfaction). For subjects in the intervention group, the second baseline visit includes attachment of accelerometer for 2 week assessment of community walking, fitting and tuning of new orthoses and shoes per AFO-FC algorithm, and gait analyses in barefoot and with AFO-FC. The intervention group return after two weeks of AFO-FC wear to check/adjust alignment using the VVGL, then wear the AFO-FC for three months before returning for their third assessment visit (T1). For subjects in the waitlist group, the second baseline visit includes fitting new TSAFO, attachment of accelerometer and gait analyses in barefoot and with TSAFO. They then wear

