We will enroll 30 ambulatory children with spastic diplegia CP, aged 4-9 years and Gross Motor Function Classification System (GMFCS) levels of II or III [41]. All participants will be clinically appropriate for a solid AFO based on physical exam/visual gait analysis criteria of: (1) insufficient gastrocnemius length to allow knee extension with ankle dorsiflexion of 10 degrees and an uncompromised foot arch; (2) low tone in the calf muscles with inability to control dorsiflexion during stance; (3) insufficient calf muscle strength to prevent excessive dorsiflexion in stance and create a 'quasi stiff' ankle in terminal stance that allows the heel to rise from the ground; and (4) insufficient triplanar boney stability of the foot during stance phase dorsiflexion [5, 6, 30]. Sample will be stratified by age (< 6 years or older) and GMFCS level. Only children with spasticity as their primary movement disorder and abnormal leg segment alignment during stance (crouch or equinus), will be enrolled to partially control for the heterogeneous clinical presentation found in this population. Elementary school age children are included, per ability to participate in the assessment sessions, yet limit fixed musculoskeletal

contractures often found in older children with CP. Participants who have undergone orthopedic or neurological surgery less than 6 months prior to enrollment or injection therapies (phenol, botulinum toxin) less than 3 months prior to enrollment will be excluded. Orthopedic and neurological surgeries as well as injection therapies are common interventions for children with CP in this age range and with these functional walking levels.

Outcomes Measures:

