AIM #2: The primary outcome of community walking activity will be captured with the ankle worn StepWatch (SW) accelerometer with balance quantified using the Pediatric Balance Scale. Parental report will capture physical activity with the Activity Scale for Kids – Performance version (ASKp), activity, fatigue and pain with selected items from the Patient-Reported Outcomes Measurement

Information System (PROMIS) and satisfaction with devices via the Orthotic and Prosthetic Users' Survey (OPUS). StepWatch (SW) – A pager sized accelerometer worn on the ankle, the SW, has one of the highest levels of accuracy for detecting steps across walking speeds from among commercially available monitors. SW daily stride levels for typical children and a large cohort with CP have been documented.

Power and Sample Size:

We will power this exploratory study based on our case series data (n=4, Fig. 5), published MCID for the Aim #1 primary outcomes of GDI and gait speed and published data for walking activity in CP [1, 45, 50]. A total sample size of 27 would allow 80% power to detect a 5 point GDI difference between groups with 97% power for a 7 point difference (MCID = 4.3 to 5.0) [45, 49] between TSAFO and AFO-FC. This sample size will have 83% power to detect a 0.10 m/sec difference in gait speed between groups with 95% power for a 0.15 difference (MCID=0.10 m/sec [50]) between conditions. A sample size of 27 has >99% power to detect a 2,000 strides/day treatment condition difference per StepWatch. This is based on the PI's cross-sectional StepWatch strides/day data from 134 youth with CP (GMFCS level II, n=84; level III, n=50; ages 2-14 years) with a mean difference between GMFCS levels of 1,630 strides (SD=2100) [1]. Therefore, we will enroll 30 participants to account for 10% attrition.

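### The SAP's >99% StepWatch power at n=27 is not supported for the planned two-group T1 regression; its own SD gives about 66% unadjusted and 78–91% at baseline correlations of 0.5–0.7

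*SAP*

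**What the plan says.** Under Power and Sample Size the SAP states: "A sample size of 27 has >99% power to detect a 2,000 strides/day treatment condition difference per StepWatch". The next sentence gives the basis as "cross-sectional StepWatch strides/day data from 134 youth with CP (GMFCS level II, n=84; level III, n=50; ages 2-14 years"). The SD is attached there to a "mean difference between GMFCS levels of 1,630 strides (SD=2100"). That is the only StepWatch SD in the SAP.

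The same section makes clear that 27 covers both groups together: "A total sample size of 27 would allow 80% power to detect a 5 point GDI difference between groups". Enrolment is set at 30 to allow for 10% attrition.

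The Analysis Plan fixes the comparison that the power should describe. For both aims, "our primary analysis will be an intent-to-treat analysis using outcomes collected during the parallel group RCT phase", before the waitlist group crosses over. It is a linear regression of the T1 outcome in which "group indicator is the predictor of interest, with including baseline outcomes, and biomarkers of age, gender, gait pattern (equinus or crouch) and GMFCS". A mixed model over T0, T1 and T2 is planned as a secondary analysis.

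The documents give no alpha, sidedness, allocation ratio or baseline-to-T1 correlation for the power calculation.

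**The concern.** A difference of 2,000 against an SD of 2,100 is a standardised effect of 2,000/2,100 = 0.95. With 13 or 14 children per group, that does not come close to 99% power unless the baseline measurement removes most of the between-child variance. The SAP assumes no such reduction. Its cited source is cross-sectional, and as described it cannot supply a correlation over time.

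Community walking is the primary outcome of Aim 2. A reader is told that the risk of missing a 2,000 strides/day effect is below 1%, and could take a null StepWatch result as strong evidence against an effect of that size. If the true risk is many times larger, that reading is wrong.

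**Working it through.** **Inputs from the SAP.** Difference 2,000 strides/day; SD 2,100; total n = 27; regression at T1 on group, baseline outcome, age, gender, gait pattern and GMFCS.

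**Assumed, because not stated.** Two-sided alpha 0.05; 1:1 allocation (13 vs 14); 2,100 is a between-child SD; baseline-to-T1 correlation r over a range. Power is from the noncentral t distribution.

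**1. Reproducing the stated figure.** Treat all 27 children as contributing a difference whose SD is 2,100. The noncentrality is 2,000/(2,100/√27) = 4.95 on 26 df, and power is 99.7%. This matches >99%, but it is a one-sample or paired test.

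**2. Two groups, unadjusted.** SE = 2,100 × √(1/13 + 1/14) = 808.8. Noncentrality = 2,000/808.8 = 2.47 on 25 df. Power is 66.2%. The difference detectable with 80% power is about 2,360 strides/day.

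**3. The planned model.** Seven parameters (intercept, group and five covariates) leave 27 − 7 = 20 residual df. The residual SD is 2,100 × √(1 − r²).

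| r | Residual SD | Power |
|---|---|---|
| 0 | 2,100 | 65.3% |
| 0.5 | 1,819 | 77.5% |
| 0.6 | 1,680 | 83.6% |
| 0.7 | 1,500 | 90.9% |
| 0.8 | 1,260 | 97.5% |
| 0.85 | 1,106 | 99.4% |

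Power reaches 99% at a residual SD of about 1,151, that is r = √(1 − (1,151/2,100)²) ≈ 0.836. If only baseline is charged a degree of freedom (24 df), the threshold is r ≈ 0.833, and power at r = 0.5, 0.6 and 0.7 is 78.2%, 84.3% and 91.3%.

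**4. More favourable readings.**

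- One-sided 5%, unadjusted: 77.6%. In the planned model: 86.7% at r = 0.5, 95.5% at r = 0.7 and 99.0% at r = 0.8.
- All 30 enrolled children analysed (15 vs 15), unadjusted: 71.2%.
- 27 per group, unadjusted, against the SAP's own use of 27 as a total: 93.0%.
- 2,100 read as the overall SD of the 134 youth, with the GMFCS gap removed by adjustment: √(2,100² − (84/134)(50/134) × 1,630²) ≈ 1,946. With 20 df, power is 71.8% at r = 0, 83.4% at 0.5, 88.7% at 0.6, 94.4% at 0.7 and 98.8% at 0.8. It reaches 99% at r ≈ 0.81.

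None of these exceeds 99% without a baseline correlation of about 0.8 or more.

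**The case against.** The best defence is that the sentence may not refer to the T1 regression. It speaks of a difference between treatment conditions, whereas the GDI sentence speaks of groups. The secondary mixed model uses a time-varying indicator under which every child moves from 0 to 1, and StepWatch is collected at T2. A within-child comparison on all 27 would give 99.7%, either with 2,100 as the SD of the difference or with a between-child SD of 2,100 and r = 0.5.

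This explains how the figure might have arisen but does not support it. The gait-speed sentence uses both expressions, so the wording settles nothing. The secondary model also includes discrete time effects. A generalised least squares calculation for it (compound symmetry, SD 2,100, 25 df) gives about 83% at r = 0.5, 95% at 0.7 and 99% at 0.8, so it does not deliver >99% at modest correlations either.

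It can also be said that a correlation or within-child SD may lie in the case-series figure or the cited sources, which are not available here. However, the SAP names the cross-sectional data as the basis of this particular figure.

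Three points stand. The range 0.5–0.7 is an assumption with no support in the documents, and higher values are not excluded. How the sponsor obtained the figure is not documented. The study is described as exploratory, and the number of children does not depend on this claim.

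**Conclusion.** The concern holds. From the stated inputs, >99% is not the power of the primary StepWatch analysis. Under two-sided 0.05, 13 vs 14 and a between-child SD of 2,100, power is about 66% unadjusted and about 78–91% for r of 0.5–0.7. The chance of missing a 2,000 strides/day effect is then about 9–22%, or about one in three if the covariates explain nothing. The stated figure is unsupported rather than impossible: it would hold at r above about 0.83–0.84.

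The meaning of the SD adds uncertainty. It is attached to a difference between GMFCS levels in youth aged 2–14, while the Participant Characteristics section says "We will enroll 30 ambulatory children with spastic diplegia CP, aged 4-9 years".

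StepWatch does not appear to drive n = 27, since the lowest power quoted is 80%, for GDI. The correction therefore concerns a stated operating characteristic and leaves the enrolment target alone.

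**What to change.** Replace the >99% figure with the power of the two-group T1 model. State alpha, sidedness, allocation, what the SD of 2,100 represents, and an assumed baseline correlation with its basis and a range. Possible wording, with the assumptions for the sponsor to confirm:

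> Assuming two-sided alpha 0.05, 1:1 allocation (13 vs 14 evaluable) and a between-child SD of 2,100 strides/day, power for a 2,000 strides/day difference at T1 is about 66% unadjusted. With covariate adjustment it is about 78–91% for a baseline-to-T1 correlation of 0.5–0.7, and exceeds 99% only above about 0.83–0.84. The unadjusted difference detectable with 80% power is about 2,360 strides/day.

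If the sponsor meant a within-child comparison, the SAP should say so, give the SD of the within-child difference, and still report power for the primary analysis.

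The SAP should also state whether the baseline StepWatch recording is made before the new device is worn. Of children randomised to AFO-FC it says: "second baseline visit includes attachment of accelerometer for 2 week assessment of community walking, fitting and tuning of new orthoses and shoes". The two-week recording may therefore be made in the new device. The adjusted figures hold only for a pre-device baseline.

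The cost is SAP wording only. No children are added and the analysis does not change; the one drawback is a less favourable stated figure.
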